9.4.2. Assessment of Severity

The severity, or intensity, of an AE refers to the extent to which an AE affects the participant's daily activities or their health. The intensity of the AE will be rated in accordance with the CTCAE Version 5.0. Adverse events related to temperature and abnormal laboratory results that are not found in the CTCAE Version 5.0 will be rated in accordance with the FDA Guidance for Industry *Toxicity Grading Scale for Healthy Adult and Adolescent Volunteers Enrolled in Preventive Vaccine Clinical Trials* [[Appendix 14.5 Toxicity Grading Scale](#)].

Changes in the severity of an AE should be documented to allow an assessment of the duration of the event at each level of intensity to be performed. Adverse events characterized as intermittent do not require documentation of onset and duration of each episode.

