9.4.4.1. Rule for Repetition of an AE

An increase in the intensity of an AE should lead to the repetition of the AE being reported with:

- The outcome date of the first AE that is not related to the natural course of the disease being the same as the start date of the repeated AE, and the outcome of "worsening".
- The AE verbatim term being the same for the first and repeated AE, so that the repeated AE can be easily identified as the worsening of the first one.

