5.3.4.2 Treatment-Emergent Adverse Events

An adverse event (AE) will be classified as ‘treatment-emergent’ if the onset date/time was on or after the start date/time of study treatment. Where dates or times are missing or partially missing, AEs will be assumed to be treatment-emergent, unless there is clear evidence (through comparison of partial dates/times, see [Section 7.3.1](#)) to suggest that the AE started prior to dosing.

AEs will be classified into the following study phases based on the onset date/time of the AE after any imputations:

- Pre-Treatment Phase: All AEs with onset date/time prior to the first dose of randomised study treatment
- Treatment Phase: All AEs with onset date/time at the time of or after the first dose of randomised study treatment (Day 1) up to and including the date of the last dose of treatment received.
- Follow-up Phase: All AEs with onset date after the date of the last dose of treatment received.

For participants who complete 16 weeks of dosing per protocol, the Treatment Phase will be from Day 1 to the Week 16 visit, and the Follow-up Phase will start after the Treatment Phase and last until their last day in the study. In all cases the day will be assumed to start at 00:00 hours and end at 23:59 hours. Adverse events occurring in both the Treatment Phase and Follow-up Phase are classified as treatment emergent.

The onset phase of all AEs will be included in the relevant data listings.

6 Sample Size

Cohorts 1-3

The sample size was calculated using the assumption that data from the placebo participants in the three cohorts can be pooled prior to comparison with the EDP1815 treatment groups. No adjustments for multiple testing have been made.

The primary efficacy endpoint is the achievement of EASI-50 at Week 16. The pooled placebo response rate is estimated to be approximately 25% and a doubling of this to 50% for EDP1815 would be considered as clinically meaningful.

Using a two-sided test at the 5% level of significance, 58 participants in each treatment group would give 80% power to detect a difference in one of the EDP1815 cohorts compared to the pooled placebo group. There would also be more than 90% power to compare the pooled EDP1815 group to the pooled placebo group.

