10.2 Adverse Events

Adverse events will be reported from the date of signed informed consent and through the Week 16 visit for participants entering the OLE study/28 days after cessation of dosing for participants who don't enter OLE. Adverse events occurring after the 28 days post-treatment would only be reported if the investigator considers it to be related to the study treatment.

Only treatment emergent AEs (TEAEs) will be included in the summaries, pre-treatment AEs will be included in the listings of all AEs.

All AEs will be coded using MedDRA. The dictionary will be updated through the life of the study with version 24.0 used initially. Severity of event will be coded using the Common Terminology Criteria for Adverse Events v5.0 (CTCAE).

An overview of TEAEs will be produced showing the number and percentage of participants with:

- Any TEAEs
- Any TEAE of CTCAE grade 2 or above
- Any TEAE of CTCAE grade 3 or above
- Any TEAE of CTCAE grade 4 or above
- Any fatal TEAE
- Any serious TEAE
- Any TEAE leading to permanent discontinuation of study drug
- Any TEAE leading to withdrawal from the study
- Any related TEAE
- Any related TEAE of CTCAE grade 2 or above
- Any related TEAE of CTCAE grade 3 or above
- Any related TEAE of CTCAE grade 4 or above
- Any related fatal TEAE
- Any related serious TEAE
- Any related TEAE leading to permanent discontinuation of study drug
- Any related TEAE leading to withdrawal from the study

Related events are those which were considered by the investigator to be possibly, probably or definitely related to study drug.

TEAEs will also be summarized by system organ class (SOC) and preferred term (PT). Summary tables will contain the number and percentage of participants and the number of events. A participant who has multiple events in the same SOC or the same preferred term will be counted only once in the participant counts but all events will be counted in the event counts. Adverse event summaries will be sorted by the internationally agreed SOC order ([Table 5](#)) and decreasing incidence of preferred term within SOC in the EDP1815 column.

Related TEAEs and TEAEs of CTCAE Grade 3 or above will also be summarized by SOC and PT in the same manner as described above.

Non-serious TEAEs will be also summarised by SOC and PT, however, PTs will be presented only in case of TEAEs reported by at least 5% of participants in any treatment group.

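### An adverse event that worsens is re-entered as a further AE, and the SAP has no rule to count the linked entries once in its event-count columns

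*SAP*

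**What the plan says.** **How worsening is recorded.** Protocol 9.4.4.1 begins: "An increase in the intensity of an AE should lead to the repetition of the AE being reported with" the attributes it then lists. The first entry's outcome is set to *worsening*, and its outcome date is specified as "being the same as the start date of the repeated AE". Both entries carry the same verbatim term, "so that the repeated AE can be easily identified as the worsening of the first one".

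**Why severity changes are recorded.** Protocol 9.4.2 gives the purpose: "Changes in the severity of an AE should be documented to allow an assessment of the duration of the event at each level of intensity".

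**What is treatment-emergent.** Under SAP 5.3.4.2 an AE is treatment-emergent "if the onset date/time was on or after the start date/time of study treatment". The test uses the onset of each AE.

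**What is tabulated.** SAP 10.2 says of the tables by system organ class and preferred term: "Summary tables will contain the number and percentage of participants and the number of events". A participant with several events in one class or term "will be counted only once in the participant counts but all events will be counted in the event counts". It then adds: "Related TEAEs and TEAEs of CTCAE Grade 3 or above will also be summarized by SOC and PT in the same manner as described above".

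**What is absent.** SAP 7.3.2, the only SAP rule on incomplete AE attributes other than dates, deals with missing relationship. No section of the SAP or its Cohort 4 addendum defines an event as anything other than an AE entry, or merges linked entries before counting.

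**The concern.** Protocol 9.4.2 treats severity changes as levels of one event, and 9.4.4.1 collects the information needed to recognise them as such. The tabulation plan does not use that link. An event count should say how many separate AEs occurred. As specified, it adds the number of times they got worse.

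The unit of counting is also uneven. Protocol 9.4.2 does not ask for the dates of each episode of an intermittent AE, so a headache that comes and goes can be a single entry. A continuous headache that intensifies once is two.

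Protocol 3.3 rests the safety evaluation on both the severity and the frequency of AEs. If AEs worsened more often in one arm, part of that difference in severity would appear in the event column as a difference in frequency, and the table would give the reader no warning.

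**Working it through.** The plan states no figure to reproduce. The check is a count by hand under the rules as written.

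**Inputs**

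- Entries per AE: one, plus one for each increase in intensity (Protocol 9.4.4.1).
- Treatment-emergence: decided entry by entry on onset date (SAP 5.3.4.2).
- Events: all counted, with no merging rule (SAP 10.2).
- Participants: counted once per class or term (SAP 10.2).

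**Formula.** If an AE starts after first dose and its intensity rises k times, entries = 1 + k, events = 1 + k and participants = 1. With linked entries counted once, events = 1 and participants = 1. If the AE starts before first dose, its first entry is not treatment-emergent, so only the entries that begin after first dose count.

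**Examples, one participant each**

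| Course of the AE | All-TEAE events, as written | All-TEAE events, linked | Grade 3+ events, as written | Participants in the all-TEAE table |
|---|---|---|---|---|
| Grade 1 to 2, after first dose | 1 + 1 = 2 | 1 | 0 | 1 |
| Grade 1 to 2 to 3, after first dose | 1 + 2 = 3 | 1 | 1 | 1 |
| Grade 3 to 4, after first dose | 1 + 1 = 2 | 1 | 2 | 1 |
| Starts before first dose, worsens once after it | 1 | 1 | 1 if the later entry is Grade 3 or above, otherwise 0 | 1 |

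The Grade 3+ table is therefore inflated only by worsening that begins at Grade 3 or above. The related table is inflated only when more than one linked entry is classed as related.

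**Size across a table.** For AEs that start after first dose, the event count divided by the number of distinct AEs is 1 + the mean number of worsenings per AE. The documents give no value for that mean. The following rates are assumptions that show only how the formula behaves:

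- 10% of AEs worsen once: 1 + 0.10 = 1.10.
- 20% worsen once and 5% twice: 1 + 0.20 + 2 × 0.05 = 1.30.
- 20% worsen once in one arm and 5% in the other, with equal numbers of distinct AEs: 1.20 / 1.05 = 1.143.

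**What does not change.** Participant numbers and percentages in these tables stay the same. The TEAE overview in SAP 10.2 counts participants only. Protocol Table 11-4 sets incidence per treatment group as the summary measure for AEs and SAEs. The halting criteria in Protocol 9.9 for related SAEs and for Grade 3 AEs are triggered by fatal cases or by numbers of participants, not by entries.

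**The case against.** The strongest reply is that nothing instructs anyone to double count. The SAP speaks of events, not entries. Protocol 9.4.2 uses the singular for an event with several intensity levels, and 9.4.4.1 makes the link easy to see. A programmer could count linked entries once and still claim to follow SAP 10.2. Part of the 9.4.4.1 wording also appears to be limited to AEs outside the natural course of the disease. Protocol 9.4.4 leaves entry details to the eCRF Completion Guidelines, which are not part of these documents. And the event columns are supplementary, with no test attached.

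Much of this stands, and it limits how much the point matters. It does not remove the gap. Protocol 9.4.4.1 calls each entry an AE, the SAP classifies each AE by its own onset, and no collapsing rule exists. Counting each entry is therefore the natural reading. If two programmers can defend different counts, the SAP needs to choose.

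Three stronger readings are tempting but not supported:

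- *AE incidence or the halting rules are inflated.* They are based on participants, as shown above.
- *An AE that turns serious is necessarily counted in both the serious and the non-serious table.* Protocol 9.4.4.1 is triggered by intensity, not seriousness, and does not say how seriousness is assigned across linked entries.
- *Event counts will be overstated by a known percentage, or will favour one arm.* The documents give no worsening rate and no reason to expect a difference between arms.

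**Conclusion.** The point holds in a narrow form and is minor. Read together, Protocol 9.4.4.1, SAP 5.3.4.2 and SAP 10.2 turn one AE with k intensity increases after first dose into 1 + k events in the all-TEAE table. The related and Grade 3+ tables are affected only where more than one linked entry qualifies. The total effect cannot be computed from the documents.

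The conclusion assumes that each entry is counted as an event and that no unseen data-entry guideline says otherwise. It touches no efficacy result and no planned inference. What is at stake is whether the event columns can be read as numbers of distinct AEs.

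**What to change.** Add a rule to SAP 10.2, for the event-count columns only. Treatment-emergent entries of the same participant count as one event when they share a verbatim term, the earlier entry has the outcome *worsening*, and its end date equals the start date of the next. That event takes the maximum grade and the strongest relationship among its entries. Recurrences without this link remain separate events.

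Leave three things on the individual entries: treatment-emergence under SAP 5.3.4.2, participant counts, and the serious or non-serious classification. The last matters because collapsing at maximum seriousness could take a participant out of the non-serious table and move a preferred term across the 5% display threshold in SAP 10.2. Keep all entries in the listings.

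The cost is a few lines of SAP text and a small linking step in the AE analysis dataset. Protocol 9.4.4.1 already has sites collect the term, outcome and dates that the link needs.

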10.3 Deaths, Serious Adverse Events and other Significant Adverse Events

Treatment emergent SAEs, TEAEs leading to discontinuation of study drug or withdrawal from the study will be summarized separately by treatment, SOC and preferred term.

Serious AEs, fatal AEs and AEs leading to discontinuation of study drug will each be listed separately by participant.

No specific adverse events are considered to be of special interest for EDP1815.

10.4 Pregnancies

Pregnancy test data will be listed only.

10.5 Clinical Laboratory Evaluations

Central laboratory data will be used for all safety laboratory evaluations. [Table 6 \(Section 25\)](#) shows the parameters which will be collected and the units in which they will be supplied. Lab data will be transformed as appropriate to the International System of Units (SI units) as part of the SDTM programming and SI units will be used for all summaries.

Haematology and chemistry parameters will be summarised by visit, including change from baseline for all post-baseline visits.

The number and percentage of participants showing shifts from baseline to worst-case post-baseline with respect to the normal ranges will also be summarised for each haematology and chemistry parameter. Categories will be:

- Low
- Normal
- High

Haematology and chemistry values will also be flagged for potentially clinically important (PCI) values if they meet any of the criteria for Grade 2 or higher events according to CTCAE V5.0. The PCI criteria are listed in [Table 6 \(Section 25\)](#). The number and percentage of participants showing shifts from baseline to worst-case baseline with respect to PCI criteria will be summarised for all parameters where PCI criteria have been defined. Categories will be:

- Low
- Within range
- High

For both the normal range and PCI summaries, the determination of worst-case post-baseline will consider both scheduled and unscheduled assessments which occur after the first dose of study treatment. Percentages will use the number of participants with at least one post-baseline assessment available as the denominator. If the baseline value is missing it will be assumed to be normal/within range. Worst-case can be either High or Low and if a participant has post-baseline values both above and below the normal range/PCI criteria then they will be counted in both relevant categories.

Haematology and chemistry data will be listed, including changes from baseline, normal ranges, flags for measurements outside the normal range, and flags for meeting PCI criteria. In addition, for participants who meet at least one PCI criteria, all values within the laboratory type (haematology or chemistry) will be listed separately.

Urinalysis data will be listed only.

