14.5. Toxicity Grading Scale

The following scales come from the FDA Guidance for Industry *Toxicity Grading Scale for Healthy Adult and Adolescent Volunteers Enrolled in Preventive Vaccine Clinical Trials*, September 2007.

Temperature Adverse Event Grading Scale

Vitals Signs*	Mild (Grade 1)	Moderate (Grade 2)	Severe (Grade 3)	Potentially Life Threatening (Grade 4)
Fever (°C)** (°F)**	38.0 – 38.4 100.4 – 101.1	38.5 – 38.9 101.2 – 102.0	39.0 – 40 102.1 – 104	> 40 >104

Laboratory Results Adverse Event Grading Scale

Serum *	Mild (Grade 1)	Moderate (Grade 2)	Severe (Grade 3)	Potentially Life Threatening (Grade 4)**
Sodium – Hyponatremia mEq/L	132 – 134	130 – 131	125 – 129	< 125
Sodium – Hypernatremia mEq/L	144 – 145	146 – 147	148 – 150	> 150
Potassium – Hyperkalemia mEq/L	5.1 – 5.2	5.3 – 5.4	5.5 – 5.6	> 5.6
Potassium – Hypokalemia mEq/L	3.5 – 3.6	3.3 – 3.4	3.1 – 3.2	< 3.1
Glucose – Hypoglycemia mg/dL	65 – 69	55 – 64	45 – 54	< 45
Glucose – Hyperglycemia Fasting – mg/dL Random – mg/dL	100 – 110 110 – 125	111 – 125 126 – 200	>125 >200	Insulin requirements or hyperosmolar coma
Blood Urea Nitrogen BUN mg/dL	23 – 26	27 – 31	> 31	Requires dialysis
Creatinine – mg/dL	1.5 – 1.7	1.8 – 2.0	2.1 – 2.5	> 2.5 or requires dialysis
Calcium – hypocalcemia mg/dL	8.0 – 8.4	7.5 – 7.9	7.0 – 7.4	< 7.0
Calcium – hypercalcemia mg/dL	10.5 – 11.0	11.1 – 11.5	11.6 – 12.0	> 12.0
Magnesium – hypomagnesemia mg/dL	1.3 – 1.5	1.1 – 1.2	0.9 – 1.0	< 0.9
Phosphorous – hypophosphatemia mg/dL	2.3 – 2.5	2.0 – 2.2	1.6 – 1.9	< 1.6
CPK – mg/dL	1.25 – 1.5 x ULN***	1.6 – 3.0 x ULN	3.1 – 10 x ULN	> 10 x ULN
Albumin – Hypoalbuminemia g/dL	2.8 – 3.1	2.5 – 2.7	< 2.5	--
Total Protein – Hypoproteinemia g/dL	5.5 – 6.0	5.0 – 5.4	< 5.0	--
Alkaline phosphate – increase by factor	1.1 – 2.0 x ULN	2.1 – 3.0 x ULN	3.1 – 10 x ULN	> 10 x ULN
Liver Function Tests –ALT, AST increase by factor	1.1 – 2.5 x ULN	2.6 – 5.0 x ULN	5.1 – 10 x ULN	> 10 x ULN
Bilirubin – when accompanied by any increase in Liver Function Test increase by factor	1.1 – 1.25 x ULN	1.26 – 1.5 x ULN	1.51 – 1.75 x ULN	> 1.75 x ULN
Bilirubin – when Liver Function Test is normal; increase by factor	1.1 – 1.5 x ULN	1.6 – 2.0 x ULN	2.0 – 3.0 x ULN	> 3.0 x ULN
Cholesterol	201 – 210	211 – 225	> 226	---
Pancreatic enzymes – amylase, lipase	1.1 – 1.5 x ULN	1.6 – 2.0 x ULN	2.1 – 5.0 x ULN	> 5.0 x ULN

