15.3 Safety

15.3.1 Tables

Number	Title	Population	Data Point Set	Programming notes
14.3.1.1.1	Overview of TEAEs	Safety	SDPS2	Include in TLR
14.3.1.1.2	Summary of TEAEs by System Organ Class and Preferred Term	Safety	SDPS2	Include in TLR
14.3.1.2	Summary of Related TEAEs by System Organ Class and Preferred Term	Safety	SDPS2	Include in TLR
14.3.1.3	Summary of TEAEs of CTCAE Grade 3 or Above by System Organ Class and Preferred Term	Safety	SDPS2	
14.3.1.4	Summary of Non-serious TEAEs Reported by at Least 5% of Participants in Any Treatment Group by System Organ Class and Preferred Term	Safety	SDPS2	
14.3.1.5	Summary of Serious TEAEs by System Organ Class and Preferred Term	Safety	SDPS2	
14.3.1.6	Summary of Fatal TEAEs by System Organ Class and Preferred Term	Safety	SDPS2	
14.3.1.7	Summary of TEAEs Leading to Permanent Discontinuation from Study Treatment by System Organ Class and Preferred Term	Safety	SDPS2	
14.3.4.1.1	Summary of Haematology Parameters	Safety	SDPS1	
14.3.4.1.2	Shifts from Baseline to Worst-case Post-Baseline with Respect to the Normal Range for Haematology Parameters	Safety	SDPS2	
14.3.4.1.3	Shifts from Baseline to Worst-case Post-Baseline with Respect to the PCI Criteria for Haematology Parameters	Safety	SDPS2	
14.3.4.2.1	Summary of Haematology Parameters	Safety	SDPS1	
14.3.4.2.2	Shifts from Baseline to Worst-case Post-Baseline with Respect to the Normal Range for Chemistry Parameters	Safety	SDPS2	

Number	Title	Population	Data Point Set	Programming notes
14.3.4.2.3	Shifts from Baseline to Worst-case Post-Baseline with Respect to the PCI Criteria for Chemistry Parameters	Safety	SDPS2	
14.3.5.1	Summary of ECG Parameters	Safety	SDPS1	
14.3.5.2	Shifts from Baseline to Worst-case Post-Baseline with Respect to the PCI Criterion for QTcF	Safety	SDPS2	
14.3.6.1	Summary of Vital Signs	Safety	SDPS1	
14.3.6.2	Shifts from Baseline to Worst-case Post-Baseline with Respect to the PCI Criterion for Vital Signs	Safety	SDPS2	

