16	Skin and subcutaneous tissue disorders
17	Musculoskeletal and connective tissue disorders
18	Renal and urinary disorders
19	Pregnancy, puerperium and perinatal conditions
20	Reproductive system and breast disorders
21	Congenital, familial and genetic disorders
22	General disorders and administration site conditions
23	Investigations
24	Injury, poisoning and procedural complications
25	Surgical and medical procedures
26	Social circumstances
27	Product issues

25 Appendix 11: Safety Laboratory Evaluations

Table 6 Safety Laboratory Parameters and Units

Category	Parameter	Conventional Unit	SI Units	PCI Criteria (SI units)	
				Low	High
Haematology	Hemoglobin	g/dL	g/L	<100 ≥20 decrease from BL	>20 increase from BL
	Hematocrit	%	L/L		
	Red blood cell count	10 ⁶ /uL	10 ¹² /L		
	White blood cell count	10 ³ /uL	10 ⁹ /L	<3	
	Platelet count	10 ³ /uL	10 ⁹ /L	<75	
	Mean corpuscular volume	fL	fL		
	Mean corpuscular hemoglobin	pg	pg		
	Mean corpuscular hemoglobin concentration	g/dL	g/L		
	Absolute neutrophils	10 ³ /uL	10 ⁹ /L	<1.5	
	Absolute lymphocytes	10 ³ /uL	10 ⁹ /L	<0.8	>4
	Absolute monocytes	10 ³ /uL	10 ⁹ /L		
	Absolute eosinophils	10 ³ /uL	10 ⁹ /L		
	Relative neutrophils	%	%		
	Relative lymphocytes	%	%		
	Relative monocytes	%	%		
	Relative eosinophils	%	%		
	Relative reticulocytes	%	%		

Category	Parameter	Conventional Unit	SI Units	PCI Criteria (SI units)	
				Low	High
Chemistry	Aspartate aminotransferase	U/L	U/L		>3xULN if BL did not exceed ULN, >3xBL if BL was above ULN
	Alanine aminotransferase	U/L	U/L		>3xULN if BL did not exceed ULN, >3xBL if BL was above ULN
	Creatinine	mg/dL	mcmol/L		>1.5xULN if did not exceed ULN, >1.5xBL if BL was above ULN
	Potassium	mEq/L	mmol/L		>5.5
	Sodium	mEq/L	mmol/L	<125	>150
	Blood urea nitrogen	mg/dL	mmol/L		
	Total bilirubin	mg/dL	mcmol/L		>1.5xULN if BL did not exceed ULN, >1.5xBL if BL was above ULN
	CRP	mg/L	nmol/L		
	Gamma-glutamyl transpeptidase	U/L	U/L		

Statistical Analysis Plan
Version 2.0, Final 16-Jan-2023

EDP1815-207

Category	Parameter	Conventional Unit	SI Units	PCI Criteria (SI units)	
				Low	High
Urinalysis	Protein	mg/dL	mg/dL		
	Blood				
	Glucose	mg/dL	mg/dL		
	Ketones	mg/dL	mg/dL		
	Bilirubin				
	pH	pH	pH		
	Nitrites				
	Specific gravity				

BL=Baseline, PCI = potentially clinically important, ULN = Upper limit of normal range.

Certificate Of Completion

Envelope Id: 745B2C54AFD341C299E23D85A1A54174
Subject: Complete with DocuSign: EDP1815-207 SAP V2.0 clean.pdf
Source Envelope:
Document Pages: 95

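### SAP Table 6 gives potassium no low limit, so the PCI shift table and PCI listing cannot flag low potassium, although SAP 10.5 promises flags at CTCAE Grade 2 or higher

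*SAP*

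**What the plan says.** SAP 10.5 sets one rule for laboratory PCI flags: haematology and chemistry values are flagged "if they meet any of the criteria for Grade 2 or higher events according to CTCAE V5.0". It then refers to Table 6 for the limits ("The PCI criteria are listed in" Table 6, in SAP Appendix 11). Shifts from baseline to the worst post-baseline value, in the categories Low, Within range and High, "will be summarised for all parameters where PCI criteria have been defined". Participants who meet at least one PCI criterion also get a separate listing of all values of that laboratory type.

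The Table 6 row for potassium reads "Potassium mEq/L mmol/L >5.5", with the Low cell empty. The row for sodium reads "Sodium mEq/L mmol/L <125 >150", with both cells filled.

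SAP 10.5 also plans a second shift summary, against the normal range, which "will also be summarised for each haematology and chemistry parameter". For chemistry this is Table 14.3.4.2.2, "Shifts from Baseline to Worst-case Post-Baseline with Respect to the Normal Range for Chemistry Parameters". The PCI counterpart is Table 14.3.4.2.3.

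**The concern.** The text promises a flag for any value that meets a Grade 2 or higher criterion, in either direction. The table to be programmed has no lower limit for potassium. Neither SAP 10.5, Table 6 nor the list of changes from the protocol (SAP 13) gives a reason.

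Worst-case change against PCI criteria for laboratory parameters is a named secondary safety endpoint (SAP 4.2; Protocol Table 11-4). A zero or empty Low category for potassium in that output could be read as no important low values, when no value could have qualified. Low potassium is a reasonable thing to look at for a product that acts in the small intestine (Protocol 4.7.2) in a trial that asks about bowel habits at every visit (Protocol 9.4.1). The documents do not, however, name an electrolyte risk.

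**Working it through.** No sample size, power or alpha figure is involved. The check sets the stated rule beside the table and follows the consequence through the planned outputs.

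**Step 1: what Table 6 can flag.**

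| Analyte | Low limit | High limit | Values never flagged |
|---|---|---|---|
| Potassium, mmol/L | none | >5.5 | everything at or below 5.5 |
| Sodium, mmol/L | <125 | >150 | 125 to 150 |

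For potassium, every low value falls in Within range, however low. This follows from the empty cell alone and needs no grading scale. The extracted row has one empty cell before >5.5, which fits a cell that is truly blank and not a conversion fault.

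**Step 2: is a blank cell part of the table's design?** Some rows are one-sided: white cells, platelets and neutrophils have a Low limit only; AST, ALT, creatinine and bilirubin a High limit only. Haemoglobin, lymphocytes and sodium have both. One-sided rows are therefore allowed, but no reason is given for making potassium one of them. The one electrolyte scale in the documents, Protocol Appendix 14.5, grades potassium in both directions, with a row for "Hypokalemia mEq/L".

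**Step 3: which outputs are affected.**
- Table 14.3.4.2.3 (PCI shifts, chemistry): the Low category for potassium cannot be filled.
- Listing 16.2.7.2.4 (chemistry PCI): a participant whose only abnormality is low potassium does not enter. One who enters for another chemistry criterion has the potassium value listed, but without a PCI flag.
- Listing 16.2.7.2.3 (all chemistry): a low value carries the out-of-normal-range flag but no PCI flag.

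**Step 4: which outputs are not affected.**
- Table 14.3.4.2.2 counts Low, Normal and High for every chemistry parameter, including unscheduled values, so low potassium and low sodium are counted by arm.
- The by-visit chemistry summaries include the minimum (SAP 8), so the lowest scheduled-visit value in each arm is reported.
- The full listings show every value.

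**Step 5: low sodium.** The CTCAE v5.0 limits are not reproduced. Appendix 14.5 gives these bands in mEq/L:

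| Grade | Low sodium | Flagged at <125? | Low potassium | Flagged? |
|---|---|---|---|---|
| 2 | 130–131 | no | 3.3–3.4 | no |
| 3 | 125–129 | no | 3.1–3.2 | no |
| 4 | <125 | yes | <3.1 | no |

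On this scale <125 is the Grade 4 boundary. The scale cannot settle the matter, for two reasons. Protocol 9.4.2 uses it only to grade adverse events, for temperature and for laboratory results that CTCAE does not cover. Table 6 was also evidently not built from it:

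| Table 6 limit | Place on Appendix 14.5 |
|---|---|
| Sodium >150 | Grade 4 |
| Potassium >5.5 | inside Grade 3 (5.5–5.6), so Grade 2 (5.3–5.4) is missed |
| Platelets <75 | inside Grade 3 (25–99) |
| Neutrophils <1.5 | Grade 2 boundary |
| White cells <3 | inside Grade 1 (2.5–3.5) |
| Lymphocytes <0.8 | inside Grade 1 (0.75–1.0) |

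The mismatches run in both directions. A mismatch for sodium therefore shows that the scales differ, not that <125 departs from CTCAE Grade 2.

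**The case against.** The strongest reply is that little is lost. Low potassium and low sodium appear in the normal-range shift table, the by-visit minima and the listings. Clinically significant laboratory abnormalities become adverse events (Protocol 9.10), are graded by CTCAE (Protocol 9.4.2) and enter the summaries by grade (SAP 10.2). There are no adverse events of special interest, and no document raises an electrolyte concern. The PCI table itself shows only Low, Within range and High, not grades.

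Most of this stands, and it limits the point. A reader might infer that the safety tables cannot show hypokalaemia at all. That is not so: only the PCI outputs fail. What the reply does not answer is that the normal-range table counts a marginal and a marked low value alike, the by-visit minima omit unscheduled values, and the adverse event route depends on the investigator's judgement. The PCI outputs are the planned display that applies a fixed threshold to everyone, and for low potassium they have none.

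A reader might also infer that <125 misses all but the most severe low sodium values. The documents do not support that. It rests on Appendix 14.5, which Table 6 does not use.

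**Conclusion.** The point holds for potassium. The PCI chemistry shift table and the PCI listing cannot flag low potassium at any severity, which does not match the rule in SAP 10.5. The size is one blank cell, with the PCI shift table and PCI flags that depend on it. Detection of low values is intact; threshold-based flagging is lost. A reversed safety conclusion is unlikely, but a named secondary safety endpoint would be reported incompletely.

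The mechanical result rests only on the Low cell being truly blank. Calling it a mismatch with the rule assumes that CTCAE v5.0 has a Grade 2 or higher criterion for low potassium that can be applied to laboratory values; the documents do not print CTCAE, so the sponsor must confirm this. Low sodium at <125 is a query, not a finding.

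**What to change.** - In Table 6, add a Low PCI criterion for potassium at the CTCAE v5.0 level stated in SAP 10.5. If the sponsor finds that CTCAE gives no usable limit, say so in a footnote and amend the rule in 10.5 to match.
- Check the low sodium limit and the remaining Table 6 limits against the same CTCAE rule, and correct any that differ. Do not import the Appendix 14.5 cut-offs: that would mix two scales in one table.
- Rerun Table 14.3.4.2.3, Listing 16.2.7.2.4 and the PCI flags in Listing 16.2.7.2.3. Rerun the haematology counterparts only if a haematology limit changes.

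The cost is one table cell, possibly a few more after the check, and a rerun of existing programs. No new data are needed. The downside is a few more flagged values to review.
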